Clinical Toxicity Grading Scales” in [Appendix C](#). For events not included in the protocol-defined grading system, the following guidelines will be used to quantify severity:

- Mild (Grade 1): Events require minimal or no treatment and do not interfere with the participant’s daily activities.
- Moderate (Grade 2): Events result in a low level of inconvenience or concern with therapeutic measures. Moderate events may cause some interference with functioning and daily activities.
- Severe (Grade 3): Events interrupt the participant’s usual daily activities and may require systemic drug therapy or other treatment. Severe events are usually incapacitating.

Relationship to Study Product: The study physician’s assessment of an AE’s relationship to study product is part of the documentation process, but it is not a factor in determining what is or is not reported in this study. If there is any doubt as to whether a clinical observation is an AE, the event should be reported. The relationship to study product must be assessed for AEs using the terms: related or not related. In a clinical trial, the study product must always be suspect. To help assess, the following guidelines are used:

- Related – There is a reasonable possibility that the study product caused the adverse event. Reasonable possibility means that there is evidence to suggest a causal relationship between the study product and the adverse event.
- Not Related – There is not a reasonable possibility that the administration of the study product caused the event.

9.2.2 **Solicited Events**

The Toxicity Grading Scales to be used to guide the grading of solicited AEs is in [Appendix C](#).

9.2.3 **Serious Adverse Events**

Serious Adverse Event (SAE): An adverse event or suspected adverse reaction is considered “serious” if, in the view of either the site principal investigator or sponsor, it results in any of the following outcomes:

- Death,
- a life-threatening adverse event*,
- inpatient hospitalization (defined by local practice as the study participant being present in the hospital greater than 24 hours) or prolongation of existing hospitalization,

- a persistent or significant incapacity or substantial disruption of the ability to conduct normal life functions, or
- a congenital anomaly/birth defect.

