9.5 Halting Rules

Further dosing of any participant only for the route (oral, SL, ID) will be halted if any of the following criteria are met. The study will be halted, and all further vaccine administration will be halted for DSMB review/recommendation if any of the following criteria are met for each route of administration:

- Any participant experiences vaccine-related SAE (e.g., excluding trauma or accident) from the time of the first study vaccination through the participant's last study visit.
- Any participant experiences an injection site necrosis within 7 days of vaccination.
- Any participant experiences an anaphylactic reaction related to vaccine occurring within 24 hours after vaccination.
- Any participant experiences urticaria, laryngospasm, bronchospasm, or anaphylaxis determined to be related to vaccine and within 7 days of vaccination.
- Any participant experiences facial nerve neuropathy, within 28 days of vaccination, confirmed by an investigator and determined to be related to vaccine.
- Any participant experiences a death for any reason excluding trauma or accident.

In addition, the study will be halted if two or more participants in the same cohort or three participants across all cohorts within a route of administration (who received at least one dose of study product) experience:

- The same severe (Grade 3) study vaccine-related local solicited event,
- The same severe (Grade 3) study vaccine-related systemic solicited event,
- The same severe (Grade 3) study vaccine-related clinical laboratory test,
- The same severe (Grade 3) study vaccine-related vital sign, or
- Any other severe (Grade 3) AE of the same system organ class

Exceptions to this would be:

- If there are obvious and acceptable physiological explanation for a Grade 3 abnormality (example, grade 3 hematuria in menstruating females)

Once a halting rule is met, further dosing of the respective route will cease, but follow-up visits may continue. An *ad hoc* DMID DSMB meeting and local DSMB meeting will be convened to discuss the halting event. If, following review by both the DMID DSMB and local DSMB, this is deemed acceptable to restart the study, the study will resume, upon DMID's approval and authorization.

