11.4.2 Safety Data

Summaries and analysis of safety data will be presented for the Safety Analysis Population.

Solicited AEs will be summarized by severity for each day after each study vaccination (Days 1-7 post each study vaccination) and as the maximum severity over all 8 days. Additionally, solicited AEs will be analyzed by taking the most severe response over the follow-up period, dichotomizing into a binary variable (none versus mild, moderate, or severe) and using standard techniques, such as exact confidence intervals, to summarize the percentage of participants reporting each symptom, any local symptom, and any systemic symptom. Summaries of solicited AEs will be presented separately for each study vaccination as well as overall study vaccinations by group.

Unsolicited AEs will be coded by Medical Dictionary for Regulatory Activities (MedDRA) for preferred term and system organ class. The number of SAEs is expected to be small in this study and will be reported by a detailed listing showing the event description, MedDRA coding, relevant dates (vaccinations and AEs), severity, relatedness, and outcome for each event. Non-serious unsolicited AEs will be summarized as number and percentage of participants reporting at least one event in each MedDRA preferred term and SOC, cross tabulated by severity and relationship to study product. Additionally, the percentage of participants and exact 95% confidence intervals of AEs in aggregate and by MedDRA categories will be computed.

Descriptive statistics for the actual values of clinical laboratory parameters and changes from baseline in clinical laboratory parameters will be presented for all measurements over time. If a participant has repeated laboratory values for a given time point, the value from the last evaluation will be used for analysis.

The number and percentage of participants who terminate the study early (withdraw) or discontinued treatment will be included in the subject disposition summary table. The reason for early termination and discontinuation of treatment will be tabulated if the number of occurrences permits. All early terminations and discontinuations will be listed showing the category (“Early Termination” or “Treatment Discontinuation”), reason, and study day.

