APPENDIX C: LABORATORY AND CLINICAL TOXICITY GRADING SCALES

Solicited Lab AEs	Grade 1 – Mild	Grade 2 – Moderate	Grade 3 - Severe
WBC, Decreased (cells $\times 10^9$ /Liter)	2.0 – 3.9	1.5 – 1.9	≤ 1.4
WBC, Increased (cells $\times 10^9$ /Liter)	11.1 – 15.0	15.1 – 20.0	≥ 20.1
ANC, Decreased (cells $\times 10^9$ /Liter)	1.0 – 1.9	0.75 – 0.99	≤ 0.74
Hemoglobin female (gm/dL)	9.0- 9.4	8.0 - 8.9	6.5 – 7.9
Hemoglobin, male (gm/dL)	10.0 - 10.9	9.0 – 9.9	7.0 – 8.9
Platelets (cells $\times 10^9$ /Liter)	100 – 149	50 – 99	≤ 49
Creatinine ($\mu\text{mol}/\text{Liter}$)	1.1 – 1.3 x ULN	>1.3 – 1.8 x ULN	>1.8 – 3.4 x ULN
ALT (SGPT) (U/L)	1.25 – 2.5 x ULN	>2.5 – 5.0 x ULN	>5.0 – 10.0 x ULN
Albumin (g/dL)	2.8 - 3.1	2.5 - 2.7	< 2.5
Total Bilirubin	1.1 to < 1.6 x ULN	1.6 to < 2.6 x ULN	≥ 2.6 x ULN

ULN = upper limit of normal, from the laboratory reference range

Clinical Sign	Normal	Mild (Grade 1)	Moderate (Grade 2)	Severe (Grade 3)
Temperature, °C	35-37.9	38.0 to 38.4	38.5 to 38.9	≥ 39.0
Tachycardia, bpm	≤ 100	101 to 115	116 to 130	>130
Bradycardia, bpm	≥ 50	45 to 49	40 to 44	<40
Hypertension, systolic, mmHg	≤ 140	141 to 150	151 to 155	>155

Clinical Sign	Normal	Mild (Grade 1)	Moderate (Grade 2)	Severe (Grade 3)
Hypotension, systolic, mmHg	≥90	85-89	80-84	<80
Hypertension, diastolic, mmHg	≤90	91-95	96-100	>100
Hypotension, diastolic, mmHg	≥60	45-59	35-44	<35
Feverishness (Chills/Shivering/Sweating)	none	Mild, but no interference with function	Some interference with daily activity	Significant interference, prevents daily activity
Fatigue (Tiredness)	Normal activity reduced slightly	Normal activity decreased 25-50%	Unable to perform daily activity	Urgent care visit or hospitalization
Malaise (General Unwell Feeling)	No interference with daily activity	Some interference with daily activity	Significant interference with daily activity	Urgent care visit or hospitalization
Myalgia (Body/Muscle Aches)	Mild, but no interference with function	Moderate, interferes with function, but not with daily activity	Severe, interferes with daily activity	Severe and disabling, unable to perform daily activity
Headache	Mild and brief or easily tolerated	Moderate with limited effect to daily activity	Severe and prevents daily activity	Urgent care visit or hospitalization
Allergic reaction	Pruritus, no rash	Localized urticaria	Generalized urticarial, angioedema	Anaphylaxis

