#### 9.3.1. Solicited Events and Symptoms

Solicited adverse events were collected pre-vaccination, 90 minutes post-vaccination following oral dosing or 30 minutes post-vaccination following SL and ID dosing, and then daily for 7 days after each vaccination and graded on a scale of 0 (none), 1 (mild), 2 (moderate) and 3 (severe). Grading scales for solicited adverse events are presented in [Table 7](#). Systemic events for the oral and sublingual routes include: fever, feverishness, fatigue, malaise, myalgia, or headache. Systemic events for the intradermal route include: fever,

feverishness, fatigue, malaise, myalgia, headache, diarrhea, nausea, vomiting, or abdominal discomfort. Local events for the oral route include: irritation of the oral cavity or tongue, diarrhea, nausea, vomiting, and abdominal discomfort. Local events for the sublingual route include: irritation of the oral cavity or tongue, facial nerve disturbance, diarrhea, nausea, vomiting, or abdominal discomfort. Local events for the intradermal route include: injection site pain, redness, swelling, bruising, itching, hypo/hyper pigmentation and induration, vesicles or hardened mass.

The proportion of participants reporting at least one solicited adverse event will be summarized for each solicited adverse event, any systemic symptom, any local symptom, and any symptoms. The 95% CI calculated using Clopper-Pearson methodology from a binomial distribution (SAS Proc Freq with a binomial option) will be presented (beginning at [Table 97](#) and concluding with [Table 104](#)).

For each systemic and local event, any systemic event, any local event, and any solicited event, the maximum severity over 7 days after each vaccination will be summarized for the Safety population. The number and percentage of participants reporting each event will be summarized by the maximum severity and treatment group, separately for each vaccination and over all vaccinations. For each event the denominator is the number of participants with non-missing data for the specific event (beginning at [Table 105](#) and concluding with [Table 112](#)).

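### The headache and myalgia grading anchors contradict their column heads, and five solicited symptoms carry a graded descriptor at level 0, so the primary reactogenicity counts may leave out mild events

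*Protocol*

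**What the plan says.** The grading table in Protocol Appendix C has four columns: Normal, Mild (Grade 1), Moderate (Grade 2) and Severe (Grade 3). SAP Table 7 repeats the layout.

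- **Headache.** "Mild and brief or easily tolerated" is under Normal, an anchor beginning with the word moderate is under Grade 1, and "Severe and prevents daily activity" is under Grade 2. Grade 3 requires urgent care or admission.
- **Myalgia.** "Mild, but no interference with function" is under Normal and "Moderate, interferes with function, but not with daily activity" is under Grade 1. An anchor beginning with the word severe is under Grade 2, and severe, disabling myalgia is Grade 3.
- **Fatigue.** A slight reduction in activity is under Normal, and inability to carry out daily activity is Grade 2.
- **Malaise and abdominal discomfort.** From Normal to Grade 3 the anchors run: no interference, some, significant, then urgent care or admission.

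Three parts of the plan use these columns. SAP 9.3.1 describes solicited events as "graded on a scale of 0 (none), 1 (mild), 2 (moderate) and 3 (severe". Protocol 11.4.2 analyses them by "dichotomizing into a binary variable (none versus mild, moderate, or severe", and SAP Table 135 heads the level-0 category No Symptoms. Protocol 9.5 halts on counts of "The same severe (Grade 3) study vaccine-related systemic solicited event", with a matching local criterion, and Protocol 5.3.3 withholds further doses on certain Grade 3 events.

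**The concern.** Occurrence of solicited events is the first primary safety endpoint in Protocol 3.2.1, so the boundary between level 0 and Grade 1 decides who counts as having had an event. For headache and myalgia, the table places an experience it calls mild on the no-event side. For the other three symptoms, level 0 is likewise not defined as absence of the symptom.

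The affected terms are a sizeable part of each list in SAP 4.5.1: 5 of 11 for oral dosing (6 systemic + 5 local), 5 of 12 for sublingual (6 + 6) and 5 of 19 for intradermal (10 + 9). Abdominal discomfort is a local event for the oral and sublingual routes, and Protocol 2.2.1 names it as a possible effect of residual enterotoxicity. SAP 4.2 says placebo recipients are not a comparison group. The absolute rates are therefore the result, and no between-arm contrast is planned in which a common grading error could cancel.

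At the upper end, the Grade 3 rules depend on where activity-limiting events are placed.

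**Working it through.** **The plan's own figures.** The only numerical design figures are the upper 95% bounds with no dose-limiting AE (Protocol 11.2; SAP Section 5). With 1 − 0.025^(1/n), they reproduce: n = 10 gives 30.8%, n = 20 gives 16.8%, n = 40 gives 8.8% and n = 60 gives 6.0%. The formula does not use the grading table and the bounds are not disputed. Neither document defines a dose-limiting AE, so whether the SAP's statement that none occurred among 40 vaccinees depends on these anchors cannot be told.

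**Row count in SAP Table 7.** Fourteen rows define Normal as none. Two use a normal range: fever (35-37.9) and diarrhea (normal or 1-2 loose stools). That leaves 21 − 14 − 2 = 5: headache, myalgia, fatigue, malaise and abdominal discomfort.

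**The same content graded differently within one table.**

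| Content of the anchor | Graded higher | Graded lower |
|---|---|---|
| "Mild, but no interference with function" | Feverishness: Grade 1 | Myalgia: Normal |
| Some interference with daily activity | Feverishness: Grade 2 | Malaise, abdominal discomfort: Grade 1 |
| Daily activity prevented | Feverishness, injection-site pain: Grade 3 | Headache: Grade 2 |
| Unable to carry out daily activity | Myalgia: Grade 3 | Fatigue: Grade 2 |

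The general scale in Protocol 9.2.1 points the same way. Its Grade 1 covers events that "Events require minimal or no treatment and do not interfere with the" participant's daily activities, and its Grade 3 covers events that interrupt them. It serves only as a comparator here, because it applies to events outside the protocol-defined grading system.

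**Effect on incidence (assumed counts).** Suppose 3 of 12 vaccinees have only mild, brief headache. Followed literally, the table reports 0/12 = 0% (exact 95% CI 0 to 26.5%). Counting them gives 3/12 = 25% (5.5 to 57.2%).

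**Effect on the halting count (assumed rates).** The cohort criterion needs two or more participants with the same event, and each cohort has 12 vaccinees (SAP 4.4.3). With independent participants and rate p for one event type whose grade turns on these anchors, P(X ≥ 2) = 1 − (1 − p)^12 − 12p(1 − p)^11.

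- p = 1%: 1 − 0.886 − 0.107 = 0.006
- p = 5%: 1 − 0.540 − 0.341 = 0.118 (from unrounded terms)
- p = 10%: 1 − 0.282 − 0.377 = 0.341

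These are the chances that enough such events occur for their grading to decide whether the cohort criterion is met. They are not estimates for this trial.

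**The case against.** Several stronger readings are tempting, and the documents do not support them.

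- **All five rows slipped by one column.** The words mild and severe are literally misplaced only for headache and myalgia, and disabling myalgia remains Grade 3. The other three rows use functional descriptors. Appendix C formally governs them, no source scale is given, and Normal is not strictly symptom-free for diarrhea either. A deliberately higher threshold for these three cannot be excluded.
- **Mild events are missing from the data.** The eCRF and memory aid are not in the documents. Protocol 9.2.2 says the scales guide grading, and SAP 9.3.1 describes levels by label. If staff graded by label, a mild headache was recorded as Grade 1, and relabelling level 0 would misdescribe correct data.
- **The halting rule failed, or a signal was hidden.** Escalation could also be stopped by any safety concern raised by the investigators, the medical monitor, the independent safety monitor or the local DSMB (Protocol 4.1). The local DSMB reviewed each cohort's safety data (SAP 6.6.1), and AEs were to be reviewed in real time (Protocol 9.6.4). A headache leading to urgent care would be Grade 3. Dosing has ended, so a corrected table cannot change past decisions.
- **Abdominal discomfort is an expected effect.** Protocol 2.2.1 lists it only as possible, and Protocol 8.1 does not anticipate that signs of enterotoxicity will be common or severe.
- **Every oddly laid-out row in Appendix C needs a change in SAP Table 7.** The allergic reaction and other illness rows look similar, but they are not solicited events and are not in that table.

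It is also fair that the study is descriptive and that three of its four primary endpoints do not use these rows. What remains is the contradiction between words and column heads for headache and myalgia, the inconsistency across rows, and a level-0 label that is untrue wherever the anchors were used, whether or not the thresholds were intended.

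**Conclusion.** The contradiction is certain for headache and myalgia. For fatigue, malaise and abdominal discomfort there is a clear inconsistency of about one grade against comparable rows, whose intent is unknown. It is not an extraction fault: every row has all its cells, and both documents agree.

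The effect on the primary endpoint is conditional. If the anchors were followed, mild headache or myalgia is reported as no event, and the any-symptom rows combine different definitions of absence. The direction is then towards lower stated reactogenicity. The size cannot be derived, because the documents give no symptom rates; the incidence example and the 0.6% to 34% range rest on assumed rates and on independence between participants. The Grade 3 rules depend on the same anchors, but nothing shows that a decision was affected.

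**What to change.** 1. The sponsor reconciles Protocol Appendix C, SAP Table 7, the severity definitions in Protocol 9.2.1, and the Grade 3 rules in Protocol 5.3.3 and 9.5. No threshold is proposed here, because that is a clinical decision.
2. Before the final analysis, establish from the eCRF whether these five symptoms were graded by the anchor text or by the column label. Protocol 8.1 says memory aids are not kept as source documents, so regrading from them cannot be assumed.
3. If grading followed the anchor text, then in SAP Tables 97-137 and Figures 238-253:
   - relabel level 0 for these symptoms so that it does not say none or No Symptoms, and print the anchor text;
   - report any local, any systemic and any symptom with and without the five;
   - show headache and myalgia Grade 2 events, whose anchors use the word severe, on a separate line without merging them with Grade 3;
   - state that level 0 can include mild events.
4. If grading followed the column label, the level-0 labels can stand, and a footnote to Table 7 should say how grading was done.

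The cost is a data-collection query, some footnotes and a few extra rows. Reactogenicity may look less favourable.

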**LIST OF ABBREVIATIONS**

AE	Adverse Event/Adverse Experience
ALS	Antibodies in Lymphocyte Supernatant
ALT	Alanine Aminotransferase, formerly called SGPT
ANC	Absolute Neutrophil Count
ASC	Antibody Secreting Cells
CI	Confidence Interval
CRF	Case Report Form
CVD	Center for Vaccine Development-Global Health
CyTOF	Cytometry by Time-of-Flight, or Mass Cytometry
DHHS	Department of Health and Human Services
DMID	Division of Microbiology and Infectious Diseases, NIAID, NIH, DHHS
dmLT	Double-Mutant Heat-Labile Toxin
DSMB	Data and Safety Monitoring Board
eCRF	Electronic Case Report Form
ELISA	Enzyme-Linked Immunosorbent Assay
ELISpot	Enzyme-Linked ImmunoSpot Assay
ETEC	Enterotoxigenic Escherichia coli
FDA	Food and Drug Administration, DHHS
HBsAg	Hepatitis B Virus Surface Antigen
HCV	Hepatitis C Virus
icddr,b	International Centre for Diarrhoeal Disease Research, Bangladesh
ICF	Informed Consent Form
ICH	International Conference on Harmonisation
ID	Intradermal
Ig	Immunoglobulin
ISM	Independent Safety Monitor
MedDRA	Medical Dictionary for Regulatory Activities
MM	Medical Monitor
NIAID	National Institute of Allergy and Infectious Diseases, NIH, DHHS
NIH	National Institutes of Health
PATH	Program for Appropriate Technology in Health, now simply “PATH”
PBMC	Peripheral Blood Mononuclear Cells

**List of Abbreviations** (*continued*)

PI	Principal Investigator
SAE	Serious Adverse Event/Serious Adverse Experience
SDCC	Statistical and Data Coordinating Center
SL	Sublingual
WBC	White Blood Cell
WHO	World Health Organization

## 1. PREFACE

The Statistical Analysis Plan (SAP) for “A Phase 1 Double-Blinded, Placebo-Controlled, Dose Escalation Study to Evaluate the Safety and Immunogenicity of Double Mutant Heat-Labile Toxin LTR192G/L211A (dmLT) from Enterotoxigenic Escherichia coli (ETEC) by Oral, Sublingual, or Intradermal Vaccination in Adults Residing in an Endemic Area” (DMID Protocol 14-0031) describes and expands upon the statistical information presented in the protocol.

This document describes all planned analyses and provides reasons and justifications for these analyses. It also includes sample tables, listings, and figures planned for the final analyses. Regarding the final analyses and Clinical Study Report (CSR), this SAP follows the International Conference on Harmonisation of Technical Requirements for Registration of Pharmaceuticals for Human Use (ICH) Guidelines, as indicated in Topic E3 (Structure and Content of Clinical Study Reports), and more generally is consistent with Topic E8 (General Considerations for Clinical Trials) and Topic E9 (Statistical Principles for Clinical Trials). The structure and content of the SAP provides sufficient detail to meet the requirements identified by the FDA and ICH, while all work planned and reported for this SAP will follow internationally accepted guidelines published by the American Statistical Association and the Royal Statistical Society for statistical practice.

This document contains four sections: (1) a review of the study design, (2) general statistical considerations, (3) comprehensive statistical analysis methods for immunogenicity and safety outcomes, and (4) a list of proposed tables and figures. Within the table, figure, and listing mock-ups (Appendices 1, 2, and 3), references to CSR sections are included. Any deviation from this SAP will be described and justified in protocol amendments and/or in the CSR, as appropriate. The reader of this SAP is encouraged to also review the study protocol for details on conduct of the study and the operational aspects of clinical assessments.

